3.3.1.3 Handling of Missing Data

If in case at any site, the device to collect participant reported outcomes are not synchronized with the real time, then baseline for the following participant reported outcomes are derived based on the date only, and not time of the assessment.

- Lupus quality of life scale
- EuroQol 5 dimensions
- Work Productivity and Activity Impairment (WPAI) – Lupus
- Medical Resource Use
- Columbia-Suicide Severity Rating Scale (C-SSRS)

In general, missing data is not imputed and is treated as missing unless specifically described in an analysis section. The following considerations are made for missing safety data, AE dates, and concomitant medication/diseases dates:

- Safety assessment values of the form '<x' or '>x' (i.e., above or below the limits of quantifications) are imputed as 'x' in the calculation of summary statistics but displayed as '<x' or '>x' in the listings.
- Adverse events that have missing causality after data querying are assumed to be related to study drug.
- For missing AE/concomitant medication/disease start dates, the following are applied:
 - Missing day: Impute the 1st of the month unless the month is the same as the month of the first dose of study drug and the end date is on or after the first dose of study drug or ongoing then impute first dose date.
 - Missing day and month: Impute 1st January unless year is the same as first dose date and the end date is on or after the first dose of study drug or ongoing then impute first dose date.
 - Missing year: Impute the year of dosing.
 - Completely missing: Impute first dose date unless the end date suggests it could have started prior to this in which case impute 1st January of the same year as the end date.

- For missing AE/concomitant medication/disease end dates, the following are applied:
 - Missing day: Impute the last day of the month unless the month is the same as that of the last dose of the study drug in which case impute the date of last dose.
 - Missing day and month: Impute 31st December unless the year is the same as that of the last dose of study drug in which case impute date of last dose.
 - Missing year: Impute the year of dosing.
 - Completely missing: Do not impute a date i.e., assume that AE/concomitant medication/disease is ongoing.

If a participant is known to have died where only a partial death date is available, then the date of death is imputed as the latest of

- the last known date to be alive + 1 from the database
- the death date using the available information provided:
 - Missing day only: Use the 1st of the month.
 - Missing day and month: Use 1st January.
 - Missing year: Impute the year of dosing.

For all missing start/end dates, flags are retained in the analysis datasets indicating where any programmatic imputation has been applied, and in such cases, any durations would not be calculated.

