4.2.3.2 Derivations

The dose of OCS at Week 40 used in the evaluation of this endpoint is the dose on the date of Week 40 + 1 day.

The date used for Week 40 is the date of last assessment used for efficacy analysis (SLEDAI-2K, PGA and BILAG) in the time window of Week 40 (as described in Section 3.3.2).

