7.4 Appendix D - Restricted and prohibited medications – Programmatic Rules

The process of identifying restricted and prohibited medication use outside of the protocol-defined guidance consists of both a programmatic identification of possible infractions of the guidance and a manual review for confirmation. The programmatic identification and associated responsibilities will be completed by the AZ Programming Team. The manual review is conducted by an AstraZeneca led Medication Review Team (MRT). The process and the remit of the MRT is outlined in the Restricted and Prohibited Medication Review Charter.

This appendix describes the programming rules to identify potential restricted medications during the study. The identified medications will be flagged for adjudication if the condition(s) is/are fulfilled and the MRT will decide if the medication is a restricted medication and hence fulfil the criteria of a intercurrent events.

Also, see details on restricted medications in CSP version 3, Section 7.7.1.

A 1 Definitions

If the condition(s) cannot be evaluated due to missing information (e.g., unknown dose or frequency), the medication will be flagged for adjudication.

All medications will be programmatically classified as “restricted (RM)” or “prohibited (PM)”. Those that do not meet the criteria will be left blank.

A 1.1 Time period of interest

An intercurrent event of restricted medication use can occur from the start date of IP, up until last dose of IP + 28 days.

Medications started prior to first dose of IP that are ongoing with no end date reported will be reviewed.

A 1.2 Start and end date of Restricted Medication Use

The start/end date of a restricted medication use is defined as start/end date of the medication as recorded in the eCRF. The start/end date will be available for each medication in the review log.

In the event of overlapping or additional dose regimen intake, the start/end date of the restricted medication use is defined as the start/end date of the overlapping or additional dose which leads to the restricted medication use.

Missing data handling related to the dates of prior or concomitant medications are detailed in Section 3.3.1.3.

A 1.3 Tapering and Duration

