will be converted to a prednisone equivalent dose by multiplying the total daily dose (in mg) of the respective medication with its corresponding conversion factor in the table below. All converted systemic steroid doses given on the same day will be summed to create the total daily dose. The oral corticosteroids (OCS) total daily dose will only include corticosteroids with the route = ORAL.

The following table gives examples of prednisone equivalent doses (e.g., 50 mg cortisone is equivalent to 10 mg prednisone).

Conversion factors to oral prednisone equivalent dose

Medication (preferred term)	Conversion factor	Numerical Conversion factor [a]
Betamethasone	10/1.2	8.3333
Betamethasone dipropionate	10/1.2	8.3333
Betamethasone sodium phosphate	10/1.2	8.3333
Betamethasone valerate	10/1.2	8.3333
Betropam	10/1.2	8.3333
Budesonide	10/2.25	4.4444
Celestona bifas	10/1.2	8.3333
Cortisone	1/5	0.2
Cortisone acetate	1/5	0.2
Cronolevel	10/1.2	8.3333
Decadron (nos)	10/1.5	6.6667
Deflazacort	1/1.2	0.8333
Dexamethasone	10/1.5	6.6667
Dexamethasone acetate	10/1.5	6.6667
Dexamethasone sodium phosphate	10/1.5	6.6667
Fludrocortisone	0	0
Fluocortolone	3	3
Hydrocortisone	1/4	0.25
Hydrocortisone acetate	1/4	0.25
Hydrocortisone sodium succinate	1/4	0.25
Meprednisone	5/4	1.25
Methylprednisolone	5/4	1.25
Methylprednisolone acetate	5/4	1.25
Methylprednisolone sodium succinate	5/4	1.25
Paramethasone	5/2	2.5
Prednisolone	1	1
Prednisolone acetate	1	1
Prednisolone sodium phosphate	1	1

[a] The prednisone equivalent total daily dose (in mg) will be calculated as total daily dose (in mg) of the respective medication multiplied with the conversion factor.

The total daily dose for other medications is derived in the same way as other corticosteroids except the standardization to an equivalent dose.

The methotrexate dose at Day 1 will be determined as the average weekly dose between ICF sign and Day 1. This will only be used in the determination of whether the methotrexate dose during the study is beyond the protocol limit.

[REDACTED]
 [REDACTED]
 [REDACTED]
 [REDACTED]
 [REDACTED]

CONFIDENTIAL AND PROPRIETARY 113 of 124

	
[REDACTED]
	
[REDACTED]

[REDACTED]	
[REDACTED]
	
[REDACTED]

[REDACTED]	
[REDACTED]
	
[REDACTED]

[REDACTED]	
[REDACTED]
	
[REDACTED]

[REDACTED]	
[REDACTED]
	
[REDACTED]

[illegible]

[illegible]

		
[REDACTED]

[REDACTED]	[REDACTED]	
[REDACTED]

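### When a steroid changeover day is unknown, the SAP's date imputation makes the old and new records overlap and then adds their doses, so the programmed OCS dose can be wrong

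*SAP*

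**What the plan says.** SAP 3.3.1.3 sets the rules for incomplete medication dates. When the day of a start date is unknown, the rule reads "Missing day: Impute the 1st of the month unless the month is the same as the month of the first dose". Under that exception the first-dose date is taken, if the record runs to that date or beyond. When the day of an end date is unknown, the rule reads "Missing day: Impute the last day of the month unless the month is the same as that of the last dose". Under that exception the last-dose date is taken. Both exceptions refer to the study product.

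Appendix D (SAP 7.4), A 1.2, adopts these rules: "Missing data handling related to the dates of prior or concomitant medications are detailed in Section 3.3.1.3". A 1.5.2 then builds the daily dose: "All converted systemic steroid doses given on the same day will be summed to create the total daily dose", with the OCS total restricted to the oral route. A 1.2 treats an overlapping record as a further intake. No visible rule ends a record when its successor begins.

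The OCS key secondary endpoint takes its dose from Appendix D (SAP 4.2.3.1). The Week 40 value "is the dose on the date of Week 40 + 1 day" (SAP 4.2.3.2).

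Three safeguards appear. Imputed dates are flagged, and "in such cases, any durations would not be calculated" (SAP 3.3.1.3). A medication review team decides whether a flagged medication is an intercurrent event (SAP 3.3.6 and Appendix D). Medical staff review a corticosteroid's daily dose when that dose is missing (A 1.5.1).

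**The concern.** A taper is a chain of records in which the end of one dose is the start of the next. The two unknown-day rules push those dates in opposite directions, so the records overlap when in truth one replaced the other. Each imputed date is plausible alone; the error comes from using both and then summing.

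The derived dose decides whether a participant is at or below 7.5 mg/day for the OCS endpoint and for LLDAS (SAP 4.2.14.1). The Day 1 OCS stratum is also derived by program from the eCRF data (SAP 4.2), and the OCS endpoint population is defined by baseline OCS of at least 10 mg/day. An inflated dose can turn a true OCS or LLDAS success into a failure, or move a participant across the 10 mg boundary.

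**Working it through.** The plan states no figure on this point to reproduce. As a check on the dose derivation, its conversion example works: 50 mg cortisone × 0.2 = 10 mg prednisone.

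**Both days unknown, at Week 40.**
- Inputs: first dose 15 January 2024 (illustrative). Week 40 is study day 281 (SAP Table 1), so 15 January + 280 days = 21 October, and Week 40 + 1 day = 22 October. The dose goes from 7.5 to 5 mg/day on an unknown October day.
- Imputed: the 7.5 mg record ends 31 October and the 5 mg record starts 1 October.
- Derived dose on 22 October: 7.5 + 5 = 12.5 mg/day. The true dose is 7.5 or 5, so the 7.5 mg threshold is met either way. The derived dose fails it.

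**One day unknown, same step.**
- New start known as 20 October, old end unknown: overlap 20 to 31 October, 12 days, which still includes 22 October.
- Old end known as 19 October, new start unknown: overlap 1 to 19 October, 19 days, which does not.

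**Do the first-dose and last-dose exceptions prevent it?** I applied the rules, with both days unknown, to every first-dose date in a three-year span (1,096 dates), nine taper visits (Weeks 8 to 40, every 4 weeks) and 15 offsets (±7 days), with last dose at Week 48: 1,096 × 9 × 15 = 147,960 cases. Neither exception ever applied. The overlap was always the full month: 28 days in 7,560 cases, 29 in 3,915, 30 in 48,600 and 31 in 87,885.

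**Does the overlap cover Week 40 + 1 day?** By nominal visit of the undated step:
- Week 40: 1,060 / 1,096 = 96.7%
- Week 36: 54 / 1,096 = 4.9%
- Week 32: 0 / 1,096

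The OCS endpoint is therefore exposed mainly to steps in the calendar month of Week 40.

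**Other steps** (protocol Table 10, dose in mg/day): 10 to 7.5 reads as 17.5; 20 to 17.5 as 37.5; 30 to 27.5 as 57.5; 40 to 35 as 75.

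**Day 1.** First dose 25 January; 5 to 7.5 mg early that month, both days unknown. The old record ends 31 January and the new one starts 25 January, the first-dose date. Derived Day 1 dose: 5 + 7.5 = 12.5 mg/day. True dose: 7.5. The participant moves into the stratum of 10 mg or more.

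**How many participants?** The documents do not allow an estimate. Purely as an illustration, assume 130 participants tapering, a quarter with a step in the Week 40 month, and 1 to 5% of steps undated: 130 × 0.25 × 0.01 = 0.3 to 130 × 0.25 × 0.05 = 1.6 participants. None of these inputs is sourced: 130 is the planned arm size, not a count of participants tapering.

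**The case against.** The strongest reply is that the trigger should be rare. Protocol 7.7.2 requires start and stop dates for permitted SLE therapy, tapering is managed at visits, and missing data are queried (protocol 9.4). The example schedule in protocol Table 10 also reaches the target well before Week 40, although investigators may vary it. This stands, and it keeps the point small.

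A reader might infer that an undated first taper step always meets the restricted-medication criterion of more than 14 days above the Day 1 dose. The documents do not support that. Durations on imputed dates are not calculated, conditions that cannot be evaluated go to adjudication, and the review team confirms each case. The rule tables are redacted, so how the screen treats an imputed overlap cannot be checked. A false sum above 40 mg/day could be flagged without any duration, but a flag is not a classification.

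A reader might also infer that the arm that tapers more is penalised more. This is not shown either: bursts and dose increases after a failed taper also create records.

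On Day 1, the requirement for two weeks of stable dosing makes an undated changeover less likely. It does not exclude one earlier in the same month, as in the example.

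These safeguards do not reach the OCS endpoint or LLDAS. Suppressing durations leaves the daily dose untouched, medication review decides restricted-medication status only, and dose review starts only when the daily dose is missing. Here it is present and wrong.

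**Conclusion.** The point holds as a narrow defect in derivation. Followed as written, the rules give a daily dose equal to the sum of two successive doses: for the whole month if both changeover days are unknown, for part of it if one is. The result is not a true doubling, and a month-long overlap needs both days missing.

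The exposed uses are the OCS key secondary endpoint, LLDAS (exploratory) and possibly the Day 1 stratum and the OCS subgroup. Restricted-medication status is less exposed. The number affected is unknown and probably low, and no direction between arms can be claimed. Key secondary p-values are nominal (SAP 3.3.4), which limits the inferential consequence. The conclusion assumes that no unseen programming specification or redacted rule already closes a record at its successor's start.

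**What to change.** Add to SAP 3.3.1.3 and Appendix D A 1.5.2, for sequential records of the same corticosteroid:

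1. An imputed end date may be no later than the day before the next record starts.
2. If both changeover days are unknown in the same month, one pre-specified common changeover date is used for both records.
3. Records that overlap only because of imputation are not summed. Records documented as concurrent still are.

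Apply this to the OCS endpoint, LLDAS and the Day 1 dose derivation. Under this rule a 10 to 7.5 mg step gives 10 or 7.5 mg/day on any day, never 17.5, and the false overlap falls from 28–31 days to none. Uncertainty about the true changeover day remains, but the derived dose is always one that was recorded.

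The cost is a few sentences before unblinding and a programming check that lists overlapping steroid records carrying an imputation flag. The flags are already planned, and no new data are needed.

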#### **4.3 Treatment period**

Procedures during the Treatment Period will be performed according to the Treatment Period Study Plan (Table 4), from Randomisation (Week 0) to Week 52. The participant-reported outcome assessments should be completed by the participant (unassisted by spouse, family members or friends) prior to all other evaluations, and prior to the infusion, as disease assessments/clinical evaluations may confound the results.

Before scheduling the Randomisation (Day 1) visit, ensure notification from the DACRT has been received, confirming that participant meets disease activity eligibility (Inclusion Criterion No. 9, 10 and 11). The DACRT will review all data necessary to characterize participant SLE in relation to the SLEDAI-2K, BILAG-2004, and PGA assessments (including central laboratory results).

On Day 1, ensure participant meets eligibility criteria, including Day 1 assessments according to the Treatment Period Study Plan (Table 4). Participants confirmed to be eligible will be randomised. Investigational medicinal product (anifrolumab or placebo) should be administered the same day the investigational medicinal product kit number is assigned and the same day all randomisation study procedures are performed.

Participants will have scheduled visits at 4-week ( $\pm 7$  days) intervals to complete protocol-specified assessments and investigational medicinal product administration according to the Treatment Period Study Plan (Table 4). From Week 4 through Week 48, Investigational medicinal product (anifrolumab or placebo) administration and required study procedures are preferred to be completed in the same day, but are also allowed to be completed within 24 hours if needed.

The last dose of investigational medicinal product will be administered on Week 48. At Week 52, participants will have an End of Treatment (EOT) visit. For participants who prematurely discontinue investigational medicinal product and are not willing to continue to participate in the study refer to Section 3.9 and Section 4.3.1.

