4.2.3 Key Secondary Endpoint - OCS

4.2.3.1 Definition

The effect of anifrolumab versus placebo on the ability to reduce the OCS dose in participants with baseline OCS ≥ 10 mg/day prednisone or equivalent will be evaluated. A maintained OCS reduction is defined as meeting all the following criteria:

- Achieve an OCS dose of ≤ 7.5 mg/day prednisone or equivalent by Week 40.
- Maintain an OCS dose ≤ 7.5 mg/day prednisone or equivalent from Week 40 to Week 52

A maintained OCS dose is defined as no dose increase (i.e., no dose greater than the dose at Week 40 + 1 day) between Week 40 + 2 days and Week 52, inclusive. The date used for Week 52 is the date of last assessment used for efficacy analysis (SLEDAI-2K, PGA and BILAG) in the time window of Week 52 (as described in Section 3.3.2). If no such assessment falls into the respective time window, then the target date for the timepoint will be used instead.

The derivation of the prednisone equivalent daily dose is given in Appendix 7.4.

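### The SAP's partial end-date rule can end a medication record before it starts, so a steroid increase between Week 48 and Week 52 may drop out of the daily OCS dose

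*SAP*

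**What the plan says.** SAP 3.3.1.3 gives one set of rules for partial AE, concomitant-medication and disease dates.

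- **End date, day missing:** month-end is used, with this exception: "the month is the same as that of the last dose of the study drug in which case impute the date of last dose".
- **End date, day and month missing:** 31 December, "unless the year is the same as that of the last dose of study drug in which case impute date of last dose".
- **End date, year missing:** the year of dosing is used.
- **End date completely missing:** no date is imputed and the record is taken as ongoing.
- **Start date:** the first-dose date is imputed only when the known month or year matches and "the end date is on or after the first dose of study drug or ongoing then impute first dose date". So the start-date rule checks the end date, but the end-date rules do not check the start date.

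The section then keeps a flag for each imputed date and states that "in such cases, any durations would not be calculated".

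Appendix D (A 1.2) brings these rules into the steroid derivations: "Missing data handling related to the dates of prior or concomitant medications are detailed in Section 3.3.1.3". Appendix D (A 1.5.2) sums converted doses given on the same day. SAP 4.2.3.1 requires "no dose greater than the dose at Week 40 + 1 day" from Week 40 + 2 days through Week 52. Protocol 4.3 says: "The last dose of investigational medicinal product will be administered on Week 48".

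**The concern.** For anyone who completes treatment, the four weeks from Week 48 to Week 52 lie after the last dose. The end-date rule pulls a record back to the last-dose date exactly when its known month or year matches. A steroid course that began in those four weeks can then have an end date earlier than its start. Summed by calendar day, such a record would cover no days and add no dose.

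The key secondary OCS endpoint fails a participant for any dose above the Week 40 + 1 day dose up to Week 52. The Week 52 LLDAS steroid criterion (SAP 4.2.14.1) looks at the days after the Week 48 visit. A late increase that disappears could turn a non-responder into a responder on either.

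The rule also works against the SAP's own cautious defaults. A completely missing end date leaves the course running, so knowing the month can yield less exposure than knowing nothing. SAP 4.2.3.3 counts a participant as not maintained when a condition cannot be evaluated, but an imputed date makes the condition evaluable.

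**Working it through.** The plan states no figure here, so there is none to reproduce. The rule was applied literally to examples and then to every calendar position.

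**Inputs.** Week 48 is Day 337 and Week 52 is Day 365 (SAP Table 1), so the gap is 365 - 337 = 28 days. The end-date rules are those of SAP 3.3.1.3.

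**Worked examples** (last dose 5 June 2024, Week 52 on 3 July 2024):

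| True course | End as recorded | Imputed end | Result |
|---|---|---|---|
| Starts 10 June | June 2024 | 5 June | Ends 5 days before it starts; covers no days |
| Starts 10 June | 2024 | 5 June | Same |
| 1 to 20 June | June 2024 | 5 June | Loses 15 days |
| Starts 10 June | July 2024 | 31 July | Not affected |

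Without the last-dose exception, the first record would end on 30 June and cover 21 days before Week 52.

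**How often the dates invert.** Every last-dose date in 2024-2025 was paired with every start from 1 to 28 days later, taken as equally likely. Given a partial end date, the share with imputed end before start is:

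| Course length | Day missing | Day and month missing |
|---|---|---|
| 1 day | 52.4% | 96.0% |
| 7 days | 33.7% | 94.4% |
| 14 days | 16.9% | 92.5% |

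Hand check of the first cell with 30-day months: the mean of min(28, 30 - d)/28 over d = 1 to 30 is 434/840 = 0.517.

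**How many records.** The documents give no rate of partial end dates. Assume 1-3% of late OCS records lack the end day. The number of late courses needed to expect one inverted record is 1/(rate × share):

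| Course length | At 3% | At 1% |
|---|---|---|
| 1 day | 1/(0.03 × 0.52) = 64 | 1/(0.01 × 0.52) = 192 |
| 7 days | 1/(0.03 × 0.34) = 98 | 1/(0.01 × 0.34) = 294 |
| 14 days | 1/(0.03 × 0.17) = 196 | 1/(0.01 × 0.17) = 588 |

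The trial plans about 260 participants, and the OCS endpoint uses only those on at least 10 mg/day at baseline.

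**The opposite error.** A month-only record that truly ended on 8 June, with last dose 20 June, is lengthened by 12 days. With first dose 5 December 2023 and last dose 5 November 2024, a taper step that ended in March 2024 but is recorded only as 2024 is carried to 5 November. Its dose is then added at Week 40, which can make a responder a non-responder.

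**Year of dosing.** From first dose to the nominal Week 48 dose is 336 days. In a 365-day year, 336/365 = 92% of first-dose dates put the last dose in the next calendar year, so the year of dosing is ambiguous for most completers.

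**The case against.** The strongest reply is that existing safeguards leave little at risk.

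- **BICLA.** A reader might infer that a late steroid course escapes the restricted-medication rule. The visible text does not support that. SAP 4.2 dates restricted-medication status from the medication's start. The period of interest already reaches past the last dose: "An intercurrent event of restricted medication use can occur from the start date of IP, up until last dose of IP + 28 days". Durations based on imputed dates are not calculated, conditions that cannot be evaluated are flagged for adjudication (Appendix D, A 1), and a review team confirms cases. The detailed rules are redacted, so complete protection cannot be confirmed, but neither can an escape be shown.
- **Direction.** A reader might infer that the error always favours response. It does not, because the same rule lengthens records that ended before the last dose.
- **OCS endpoint.** Restricted-medication use is also non-response here, and a course already under way at the last dose still shows its higher dose before the cut. Only courses that start after the last dose and invert matter. This stands, with one limit: a rise above the Week 40 dose that stays at or below the Day 1 dose does not meet the two OCS-dose items in Protocol 7.7.1.3. Protocol 7.7.3.3 treats increases after Week 40 as non-response, with exceptions, but how that is programmed is not visible.
- **Data quality.** Protocol 7.7.2 requires stop dates for SLE therapy, Protocol 9.4 has impossible or missing data queried, and medications are reviewed again at both follow-up visits. These lower the number of partial dates.
- **AEs.** SAP 4.6.2.1 allocates AEs by onset date, so the harm is mainly an impossible end date.

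None of this removes the defect: the rule as written can produce an end date before the start date.

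**Conclusion.** The rule is wrong as written, and the practical effect is probably very small. Its clearest reach is the programmatically derived daily OCS dose after Week 48, which feeds the key secondary maintained OCS reduction and the exploratory Week 52 LLDAS.

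The inversion shares hold only given a partial end date in the stated form and starts spread evenly over the 28 days. The 52% figure is for 1-day courses and should not be applied to longer ones. Loss of the dose is a possible result, not a stated one, because the SAP does not say how a record with end before start is processed.

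A reader might infer that several participants would be misclassified. The documents give no rate to support that. Under the assumed 1-3%, even one inverted record with a missing end day needs about 64 to 588 late OCS courses.

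**What to change.** In SAP 3.3.1.3:

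1. Remove the last-dose exception from both partial end-date rules. Impute the last day of the month, or 31 December when the month is also missing.
2. Cap the imputed date at study end or the day before the next record of the same drug.
3. Never impute an end date before the record's start date.
4. Replace the year of dosing, for a missing end year, with the earliest year consistent with the start date.

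This errs towards longer records, in line with treating completely missing end dates as ongoing. A year-only record that ended early can still be lengthened, so the cap at the next record of the same drug is needed.

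The cost is a few lines of SAP text and a small programming change. Protocol 8.1 allows documented SAP amendments before unblinding.
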